4.1 Pathology Review

Representative slides from the resected tumor will be evaluated by [name], Pathology, DHMC, for assignment of histologic grade. A report from the Department of Pathology at the institution where the resection was performed must include a determination as to whether negative margins were achieved, a measurement of the distance to the closest margin, and tumor size. Patients with initially positive margins who have been re-resected with negative margins will be eligible.

4.2 Pretreatment data to be submitted

Patient name

Patient birth date and age at diagnosis

History, noting presence or absence of prior breast surgery, irradiation and breast malignancies

Location of tumor in the breast and side affected (left/right)

Operative report from the tumor excision

Pathology report from the tumor excision, with information on margins and tumor size, as described in section 4.1

Bilateral mammogram report

Ultrasound report, if obtained

MRI report, if obtained.

Referring physician, surgeon, radiation oncologist and treating institution

5.0 RADIATION THERAPY

Radiation therapy will be administered in the vicinity of the center where the surgical resection was performed. Adjuvant radiation must start within 12 weeks of breast excision or reexcision. External beam partial breast radiation will be administered per guidelines used in the NSABP B-39/RTOG 0413 protocol.

5.1 PBI by 3D conformal external beam radiotherapy (3D-CRT)

5.1.1 Imaging

Treatment planning must be performed using a CT scan with less than or equal to 0.5cm slice thickness and extending superiorly from the mandible to below the inframammary fold inferiorly. The treatment planning scan should include the entire both lungs.

5.1.2 Target volumes

Lumpectomy cavity will be outlined based on visualization of the cavity on CT scan with or without the assistance of surgical clips.

Clinical Target Volume (CTV) is defined by expansion of the lumpectomy cavity by 15mm, but limited to 5mm of skin surface and will not include the chest wall and pectoralis muscle.

Planning Target Volume (PTV) accounts for treatment position uncertainty and will be defined as a 10mm expansion on the CTV.

PTV_EVAL excludes the expansion outside of the patient and the first 5mm of tissue under the skin and excludes chest wall, pectoralis muscle and lung.

5.1.3 Beam angles/treatment planning

Beam arrangements are at the discretion of the treating oncologist. 3, 4, or 5-filed non-coplanar beam arrangements are recommended. No electrons can be used. High-energy photons

can be used. No beams can be directed towards critical structures including heart, lung or contralateral breast. The PTV (not the PTV EVAL) will be used to plan the beam apertures.

5.1.4 Dose prescription

A total dose of 38.5 Gy will be prescribed to the isocenter given in two fractions per day of 3.85 Gy for ten fractions with at least 6 hours between fractions. Treatment will be initiated within 12 weeks of surgery and completed within 10 days of the first fraction.

5.1.5 Dose limitations (as per NSABP B-39)

Univovled normal breast- <60% whole breast reference vol should receive >50% of prescribed dose (1925cGy) and <35% should receive prescribed dose.

Contralateral breast- <3% of prescribed dose (115cGy) to any point Ipsilateral lung- <15% of the lung can receive 30% of prescribed dose (1155cGy)

Contralateral lung- <15% of the lung can receive 5% of the prescribed dose (192.5cGy)

Heart (right-sided lesions)- <5% should receive 5% of prescribed dose (192.5cGy)

Heart (left-sided lesions)- Volume receiving 5% of prescribed dose (192cGy) < 40%

Thyroid- max point dose 3% of prescribed dose (115cGy)

5.1.6 Treatment verification

Prior to delivery of the first treatment, portal films or images of each beam and an orthogonal pair will be obtained. An orthogonal pair film or image will again be obtained prior to the 5th treatment. Additional treatment verification films will be at the discretion of the local treating physician.

5.1.7 Plan evaluation

Dose volume histograms must confirm that 90% of the prescribed dose covers at least 90% of the PTV_EVAL. The maximum dose cannot exceed 120% of prescribed dose.

5.3 Radiation Therapy Quality Assurance

5.3.1 Physicians approved by RTOG for PBI

The RTOG has an approval process for radiation oncologists who are participating in NSABP B-39. This requires each investigator to submit 5 PBI plans for central review. If an investigator

has been RTOG approved for PBI, then plans will not have to be submitted to [name] prior to treatment on this protocol D0929.

5.3.2 Physicians not approved by RTOG for PBI

For radiation oncologists who have not been RTOG approved, the radiation treatment plan will be submitted to [name] for review and approval prior to initiation of radiation therapy. The following criteria will be used:

5.3.2.1 External Beam PBI

Dose volume histograms (DVHs) for the PTV_EVAL, designated critical structures and unspecified tissues will be judged as acceptable if:

- 1. DVH analysis of the target volume confirms 90% of the proscribed dose covers 90% of the PTV EVAL.
 - 2. Critical normal tissue DVHs are \leq 5% of specified value.
 - 3. Maximum dose does not exceed 120% of prescribed dose.
- 4. Dose to be delivered twice a day for a total of 10 treatments over a period of 5 to 10 days.

Dose volume histograms (DVHs) for the PTV_EVAL, designated critical structures and unspecified tissues will be judged as unacceptable if:

- 1. DVH analysis of the target volume confirms 90% of the proscribed dose covers \leq 90% of the PTV_EVAL.
 - 2. Critical normal tissue DVHs are \geq 5% of specified value.
 - 3. Maximum dose exceeds 120% of prescribed dose.
 - 4. Dose to be delivered over a period of time > 10 days.

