3.0 PATIENT SELECTION

3.1 Eligibility Criteria

3.11 Histologic proof of phyllodes tumor of borderline or malignant grade, as first defined by Pietruszka and modified by Azzopardi and adopted by the World Health Organization (1,2,17):

Borderline malignant: 5-9 mitoses/10 HPF, pushing or infiltrating margins, 2+ (moderate) stromal cellularity and atypia.

Malignant: 10 or more mitoses / 10 HPF, predominantly infiltrating margins, usually 3+ (severe) stromal cellularity and atypia but occasionally 2+.

- 3.12 The tumor has been excised with a breast-conserving resection and there is no tumor seen at any of the margins of the resection.
- 3.13 No prior breast carcinoma or ductal carcinoma in situ in the ipsilateral breast. Patients with a local recurrence of a previously excised phyllodes tumor are eligible if the recurrence is in the area of the previous excision.
 - 3.14. No history of irradiation of the ipsilateral breast.
- 3.15 No evidence of other areas worrisome for cancer on physical examination and mammography of the ipsilateral breast.
 - 3.16 Age \geq 18 years.
 - 3.17 Informed consent
 - 3.18 Documentation that either: 1) the patient's medical insurance company has certified that they will pay for the cost of radiation therapy treatments, or 2) a letter from the patient indicating that they explicitly understand the costs of radiation therapy and that the sponsor (Principal Investigator) of this study will not be held responsible for these costs.

3.2 Exclusion Criteria.

- 3.21 Histologically positive margins.
- 3.22 Breast carcinoma or ductal carcinoma in situ in the ipsilateral breast.
- 3.23 A history of irradiation to the ipsilateral breast.
- 3.24 Pregnancy. A urine pregnancy test will be performed on each fertile premenopausal female prior to entry into the study. Patients with childbearing potential must employ effective contraception during the radiation therapy.
- 3.25 A radiation planning CT scan which demonstrates a target lumpectomy cavity that is not clearly delineated or a target lumpectomy cavity/whole breast reference volume > 30%.

3.26 Unacceptable radiation therapy quality assurance parameters, as defined in Section 5.

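### Read literally, criterion 2 in Section 5.3.2.1 sets normal-tissue ceilings at one-twentieth of the Section 5.1.5 limits; the intended tolerance is not stated

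*Combined protocol and SAP*

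**What the plan says.** Section 5.1.5 sets the normal-tissue limits. Examples are "Ipsilateral lung- <15% of the lung can receive 30% of prescribed dose (1155cGy"), "Heart (right-sided lesions)- <5% should receive 5% of prescribed dose (192.5cGy") and "Contralateral breast- <3% of prescribed dose (115cGy) to any point". For the treated breast it says "Univovled normal breast- <60% whole breast reference vol should receive >50% of prescribed dose (1925cGy) and <35% should receive prescribed dose".

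Section 5.3 then divides plans by physician. Under 5.3.1, if the investigator "has been RTOG approved for PBI, then plans will not have to be submitted to" the central reviewer before treatment, no prior check takes place. Under 5.3.2, all other radiation oncologists submit the plan for approval before treatment, and 5.3.2.1 gives the criteria. Criterion 2 for acceptance is "Critical normal tissue DVHs are \leq 5% of specified value". Criterion 2 for rejection is "Critical normal tissue DVHs are \geq 5% of specified value". Neither line cites 5.1.5 or describes the 5% as a tolerance.

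Exclusion 3.26 removes patients with "Unacceptable radiation therapy quality assurance parameters, as defined in Section 5".

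**The concern.** Five percent of a limit is a very different thing from within five percent of a limit, and the text says the former. Taken at its word, criterion 2 would reject plans that 5.1.5 allows. These criteria decide plan approval under 5.3.2. Because 3.26 uses the same word, unacceptable, and points to Section 5, they also bear on eligibility.

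The risk runs in two directions. A reviewer who follows the text would turn away compliant plans. A reviewer who sensibly ignores it would apply a tolerance that is written nowhere, so a later auditor could not tell which plans met the protocol.

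**Working it through.** **Inputs.** The prescribed dose is 38.5 Gy = 3850 cGy (5.1.4). The limits are those in 5.1.5. The factor is 5% = 0.05 (5.3.2.1, criterion 2).

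**Step 1: reproduce the plan's own dose figures.** 0.50 × 3850 = 1925 cGy; 0.30 × 3850 = 1155 cGy; 0.05 × 3850 = 192.5 cGy; 0.03 × 3850 = 115.5 cGy. These match 5.1.5 apart from truncation (115.5 is printed as 115, and 192.5 once as 192). The limits themselves are therefore consistent with the prescription.

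**Step 2: apply criterion 2 as written, and as a tolerance.** Literal ceiling = 0.05 × limit. Relative tolerance = 1.05 × limit. Absolute tolerance = limit + 5 percentage points.

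| Structure (5.1.5) | Limit | Literal ceiling | Relative 5% | Absolute 5 points |
|---|---|---|---|---|
| Ipsilateral lung at 30% of dose | 15% | 0.75% | 15.75% | 20% |
| Contralateral lung at 5% of dose | 15% | 0.75% | 15.75% | 20% |
| Heart, right-sided lesion, at 5% of dose | 5% | 0.25% | 5.25% | 10% |
| Heart, left-sided lesion, at 5% of dose | 40% | 2% | 42% | 45% |
| Uninvolved breast above 50% of dose | 60% | 3% | 63% | 65% |
| Uninvolved breast at full dose | 35% | 1.75% | 36.75% | 40% |
| Contralateral breast and thyroid, point dose | 115.5 cGy | 5.8 cGy | 121.3 cGy | not computed |

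The ratio of limit to literal ceiling is 1/0.05 = 20 in every row.

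**Step 3: test one plan.** Suppose 10% of the ipsilateral lung receives 30% of dose. Under 5.1.5, 10% < 15%, so it passes. Under literal criterion 2, 10% > 0.75%, so it is unacceptable. Under either tolerance reading (15.75% or 20%) it passes, as does every plan that meets 5.1.5.

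**Step 4: check whether one misread symbol could explain this.** The phrase stands in both lists with opposite signs. Replacing the signs with strict inequalities leaves the threshold at 5% of the limit, so the result does not depend on how the symbols were read from the PDF.

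**Step 5: check the boundaries.** With the signs as they stand, a value of exactly 5% of the limit meets both the acceptance and the rejection criterion. Criterion 1 has a similar fault: 5.1.7 requires coverage of at least 90% of PTV_EVAL, but the rejection list in 5.3.2.1 takes in coverage of exactly 90%.

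**The case against.** The strongest reply is that no radiation oncologist would apply a ceiling of 0.75% of lung or 0.25% of heart. Such figures would make 5.1.5 pointless, so the reviewer surely reads the line as a tolerance. That is probably right about practice, and it limits the consequences. It does not settle what the limit is: relative and absolute readings differ (lung 15.75% or 20%; right-lesion heart 5.25% or 10%), and the text supports neither over the other. Section 5.0 refers to the NSABP B-39/RTOG 0413 guidelines, which may state a tolerance, but they are not reproduced here.

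Three further objections stand in part.

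- The link from the specified values to 5.1.5 is an inference. It is a reasonable one, since 5.1.5 holds the only normal-tissue values in the document, but 5.3.2.1 does not cite it.
- Which tissues count as critical is not fully defined. Section 5.1.3 names heart, lung and contralateral breast in an open list, so the uninvolved-breast and thyroid rows rest on a further assumption. The lung and heart rows do not.
- A reader might infer that patients with compliant plans are being excluded. The documents do not show that. Nothing in 5.3.2 forbids revising and resubmitting a plan, and 3.26 does not say that a single rejected plan ends eligibility. A plan below 5% of the limit on every structure would also pass as written.

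**Conclusion.** The point holds as a drafting error in an operative criterion. Taken literally, and assuming that the specified values are the 5.1.5 limits, criterion 2 is 20 times stricter than the limits it appears meant to enforce, and its two lists overlap at the threshold.

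Two stronger readings are not supported. One is that compliant plans are in fact rejected: that would follow only if the central reviewer applied the literal wording, which is unlikely. The other is that a 5% relative tolerance is the established intent: a tolerance of some kind is probable, but its form is not stated.

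The reach is limited to plans from physicians without RTOG approval. Their share is not given, so the number of plans affected cannot be estimated. Severity is minor: no endpoint, alpha, power or sample size changes.

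**What to change.** Reword criterion 2 in both lists of 5.3.2.1 so that it cites 5.1.5.

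- **Default, adding no new tolerance.** Accept: *All critical normal tissue DVHs meet the Section 5.1.5 limits.* Reject: *Any critical normal tissue DVH does not meet the Section 5.1.5 limits.*
- **Only if the radiation oncology lead confirms that a 5% tolerance was intended.** Accept: *Critical normal tissue DVHs do not exceed the Section 5.1.5 limit by more than 5%.* Reject: *Any critical normal tissue DVH exceeds the Section 5.1.5 limit by more than 5%.* State whether the 5% is relative or in absolute percentage points. If absolute, say how it applies to the point-dose limits.

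Either version removes the overlap at the threshold. In the same edit, change the rejection boundary in criterion 1 to coverage below 90%, in line with 5.1.7.

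Leave the reference to Section 5 in 3.26 as it is. Pointing it to the list in 5.3.2.1, which sits under the heading for physicians without RTOG approval, could leave unclear whether the exclusion still applies to other patients.

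The cost is a wording amendment to three lines of 5.3.2.1 and one question to the radiation oncology lead. It needs no new procedure, data or submission, and the exemption in 5.3.1 is untouched.

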6.0 POST-THERAPY EVALUATION

All patients will be encouraged to perform monthly breast self examination and will be followed with physical exams of the affected breast by their surgeon or radiation oncologist. These physical exams should occur every 6 months (+/- 3 months) after the initial resection through year 5 (ie. at 6,12,18,24,30,36,42,48,54,and 60 months) and then every 12 months (+/- 3 months) years 5 through 10 (ie. 72, 84, 96,108 and 120 months). Mammograms will be obtained at 6 months (+/- 3 months) and 12 months (+/- 3 months) and then annually for 10 years after the initial resection. A 5 year minimum follow-up should detect almost all recurrences, since the

vast majority of local recurrences occur within 2 years of initial excision. Since it is possible that radiation therapy may delay, but not prevent recurrences, we propose a 10 year follow-up. Suspicious masses discovered by physical exam or by imaging studies will be biopsied per routine clinical care. Biopsy proven phyllodes tumor recurrences should be reported promptly to the Principal Investigator. Patients will be terminated from the study at the time of death or after 10 years of follow-up, whichever comes first.

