In 1998 we initiated a prospective single arm study (DMS 9801) to determine whether adjuvant radiation therapy after breast conserving resection of borderline and malignant

phyllodes tumors decreases the local recurrence rate (5). Forty six women were treated at 30 different institutions. The mean patient age was 49 years (18-76). Thirty patients (65%) had malignant phyllodes tumors, the rest were borderline malignant. The mean tumor diameter was 3.7 cm (0.8-11 cm). Eighteen patients had a negative margin on the first excision. The median size of the negative margin was 0.35 cm (range <0.1-2 cm). Twenty eight patients underwent a re-excision because of positive margins in the initial resection. Two patients died of metastatic phyllodes tumors. With a median follow-up of 56 months (range 12-129 months), none of the 46 patients developed a local recurrence (local recurrence rate zero (95% CI 0 - 8%)). We concluded that adjuvant radiation therapy decreased the local recurrence rate after breast conserving resections of phyllodes tumors.

A recent retrospective report from the Rare Cancer Network also provides strong support for the use of adjuvant radiation therapy after resection of phyllodes tumors (4). Of 159 patients with borderline or malignant phyllodes tumors, 109 were treated with breast conserving surgery and 50 underwent mastectomy. Thirty six received adjuvant radiation therapy. When all 159 patients were considered the percentage free of local recurrence at 10 years in the group that received radiation therapy was significantly better than the group that did not receive radiation therapy (86% vs 59%, p= 0.02). Of the 109 patients treated with breast conserving surgery, 11 underwent radiation therapy and 68% were free of local recurrence at 10 years compared to 54% of the 98 patients who underwent lumpectomy without radiation therapy. Of the 50 mastectomy patients, 25 underwent radiation therapy and 92% were free of local recurrence at 10 years, compared to 78% of the patients undergoing mastectomy without radiation therapy. While the trends in each of these subgroups favor radiation therapy, the differences were not statistically significant. In multivariate analysis the only favorable independent prognostic factor was the use of radiation therapy.

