8.1 Statistical analysis

The rate of in-breast recurrence will be calculated with an exact binomial confidence interval. A binomial test (i.e., one sample proportion test) will be used to compare this rate to the rate of 21% determined from the literature for margin negative breast conserving resection alone. To address the secondary aim the rate from this study will be compared to the rate (0/46) obtained in the study using adjuvant whole breast radiation using a Fisher's exact test.

Additional analysis will include descriptive summaries of adverse events, time to recurrence and survival. Time to recurrence and survival will be estimated separately for the borderline and malignant tumor groups using the product limit method.

Sample Size and Power Considerations

A total sample of 50 patients will be enrolled and followed for recurrence. This yields sufficient power (i.e., 80%) to detect that adjuvant partial breast radiation is better than margin negative breast conserving resection alone, if indeed this adjuvant therapy reduces the rate to 6% or less, and the rate with resection alone is 21%. This calculation sets the type I error rate (α) at the usual 0.05. The 95% exact binomial confidence interval has an expected range of 1% to 15% if the actual rate is 5% (whereas it is 0% to 8% if the actual rate is 1%, and it is 4% to 22% if the actual rate is 10%). In comparison to the adjuvant whole breast radiation in which our prior study found no in-breast recurrences in 46 women, partial breast radiation will be identified as having a significantly higher rate if its actual rate is 15% or higher (assuming an α =0.5, and use of a Fisher exact test).

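### Scheduled follow-up runs from the initial resection, which read literally uses up part of it before treatment for patients enrolled with a recurrence; time to recurrence has no stated origin

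*Combined protocol and SAP*

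**What the plan says.** Section 6.0 sets the exam schedule: "These physical exams should occur every 6 months (+/- 3 months) after the initial resection through year 5", then yearly to month 120. Mammograms are at 6 and 12 months and "then annually for 10 years after the initial resection". The sentence that ends participation names no starting date: "Patients will be terminated from the study at the time of death or after 10 years of follow-up". The section justifies these lengths in two ways. Five years should catch nearly all recurrences, and ten years guards against radiation merely postponing them.

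Two eligible groups can have had more than one operation:

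- Section 3.13: "Patients with a local recurrence of a previously excised phyllodes tumor are eligible", provided the recurrence lies in the area of the earlier excision. No maximum interval is given.
- Section 4.1: "Patients with initially positive margins who have been re-resected with negative margins will be eligible".

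Section 5.0 uses a different clock for treatment: "Adjuvant radiation must start within 12 weeks of breast excision or reexcision".

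Section 8.1 plans the time-to-event summaries: "Time to recurrence and survival will be estimated separately for the borderline and malignant tumor groups", by the product-limit method. It does not say from which date time is counted.

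**The concern.** The anchor in Section 6.0 does not fit every patient whom Sections 3.13 and 4.1 admit. For a patient with one margin-negative excision, the first operation and the operation before radiation are the same. For a patient enrolled with a recurrence, the first operation may be years earlier. Taken at its word, Section 6.0 then starts her schedule before the tumor under study was removed. Part or all of the intensive phase is over before she is treated, and her last scheduled exam and mammogram come early.

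Two things are at stake. The first is the length of post-treatment observation, on which Section 6.0's own five-year and ten-year reasoning depends. The primary endpoint is a simple proportion with no fixed assessment time, so shorter observation can only miss recurrences. The second is the recurrence curve. An analyst looking for a time origin finds none in Section 8.1, and the nearest one in the protocol is the anchor in Section 6.0.

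**Working it through.** **1. Meaning of the anchor.** The Introduction, describing DMS 9801, separates the first operation from the later one: "Twenty eight patients underwent a re-excision because of positive margins in the initial resection". Its literature review likewise uses *initial* for the operation that preceded a recurrence. Section 5.0 names both operations where either may apply. In the protocol's own usage, then, the Section 6.0 anchor is the first operation. For a patient enrolled with a recurrence it is undefined: it could be the original surgery or the first resection of the recurrence.

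**2. Scheduled follow-up left under the literal reading.** Let *g* be the months from the first resection to the qualifying resection. The documents do not give *g*, so the values below are assumptions. Scheduled exams fall at 6, 12, …, 60 months (10 exams) and at 72, 84, 96, 108 and 120 months (5 exams), 15 in all. Time left is 120 − *g*; exams left are those dated after *g*.

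| *g* (months, assumed) | Months left | Exams left |
|---|---|---|
| 0 | 120 | 15 |
| 24 | 96 | 6 + 5 = 11 |
| 60 | 60 | 0 + 5 = 5 |
| 120 or more | 0 | 0 |

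The ten-year follow-up is shortened at any *g* > 0. The five-year minimum fails when 120 − *g* < 60, that is, when *g* > 60.

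**3. Share of eventual recurrences falling inside the schedule.** For illustration, assume exponential times from the qualifying resection with median *m*: share = 1 − 2^(−(120 − *g*)/*m*). The Introduction reports medians of 24 months or less in all but one study; 60 months is an added assumption, standing for delay by radiation.

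| *g* | *m* = 24 | *m* = 60 |
|---|---|---|
| 0 | 1 − 2^(−5) = 96.9% | 1 − 2^(−2) = 75.0% |
| 3 | 1 − 2^(−4.875) = 96.6% | 1 − 2^(−1.95) = 74.1% |
| 24 | 1 − 2^(−4) = 93.8% | 1 − 2^(−1.6) = 67.0% |
| 60 | 1 − 2^(−2.5) = 82.3% | 1 − 2^(−1) = 50.0% |

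These losses apply only to affected patients. At the five-year mark of the schedule, with *m* = 24, the share falls from 1 − 2^(−60/24) = 82.3% at *g* = 0 to 1 − 2^(−36/24) = 64.6% at *g* = 24, and to none at *g* = 60.

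**4. Re-excised patients.** In DMS 9801, 28/46 = 61% were re-excised, so this group may be large. The gap has no stated cap but is probably weeks to a few months (assumption). A gap of 3 months costs 0.3 points (*m* = 24) to 0.9 points (*m* = 60) in the table above, and it sits within the ±3-month visit window.

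**5. Product-limit curve.** Suppose the Section 6.0 anchor were reused. At time *t* the risk set of size *n* would include *k* patients who on that clock are not yet enrolled and cannot have a study event. The increment would be *d*/*n* where the patients actually under observation give *d*/(*n* − *k*). The ratio (*n* − *k*)/*n* is below 1 whenever *k* > 0, so the curve is too favourable. Neither *k* nor the distribution of *g* is given, so the size cannot be computed.

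**6. Primary design.** With N = 50, 21% against 6% and two-sided α = 0.05 (sidedness is not stated), the exact binomial rule rejects at 4 or fewer recurrences, with lower-tail α 0.0123 and power 82.1%. This agrees with the stated 80%. No term in it depends on the time origin.

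**The case against.** The strongest reply is that the harmful reading is not the intended one. Section 6.0 is headed as post-therapy evaluation and relies on a five-year minimum. The surgical clocks in Sections 5.0 and 5.1.4 can only mean surgery for the current tumor. Section 4.2 collects the operative report of the tumor excision, but for earlier breast surgery it lists only whether there was any, so the date that the literal clock needs is not among the listed items. This stands as evidence that the wording is ambiguous. It does not remove the ambiguity, because the protocol's own usage points the other way.

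A reader might infer that the plan builds guaranteed event-free time into the analysis. The documents do not support that: Section 6.0 is a visit schedule, and Section 8.1 names no origin. The bias is a risk if the anchor is carried over. Nor do they support saying that every patient leaves the study ten years after the first operation. That limit is explicit for mammograms and implied by the month-120 exam, but the termination sentence has no start date.

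It is also fair that the curves are descriptive, with no comparator curve or decision rule, while the primary analysis is a binomial proportion and the secondary comparison a Fisher exact test. And a 24-month gap still leaves 96 months, well above the five-year minimum.

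**Conclusion.** The point holds in a limited form. The Section 6.0 anchor is undefined for patients enrolled with a recurrence and, read literally, shortens their scheduled post-treatment follow-up. It undercuts the ten-year follow-up at any gap and the five-year minimum once the gap exceeds 60 months. It also does not match the clock in Section 5.0. For re-excised patients the effect is probably negligible.

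Section 8.1 omits a time origin. Borrowing the Section 6.0 anchor would bias the descriptive recurrence curve in favour of the treatment. The number of affected patients and their gaps are not in the documents, so no net bias can be stated; the capture figures are illustrations under assumed gaps and exponential recurrence times. The primary proportion is touched only through length of observation. Sample size, power and the form of the test stand. The gap is worth closing because doing so is cheap, although the main inference does not turn on it.

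**What to change.** Reconcile the anchor in Section 6.0 with Sections 3.13, 4.1 and 5.0, so that the five-year and ten-year follow-up refer to surgery for the tumor that made the patient eligible. Give the termination sentence the same starting date.

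In Section 8.1, state that time to recurrence is measured from the final margin-negative resection of the qualifying tumor. State also that patients enter the risk set at study entry or at the start of radiation, naming which (delayed entry). A resection origin keeps the curve comparable with the literature timing in the Introduction, which is counted from surgery.

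The cost is about one sentence in each section. The operative and pathology reports of the tumor excision (Section 4.2) and the radiation treatment data (Section 7.0) are already collected. Visit frequency and sample size do not change. The one downside is that some patients enrolled with a recurrence would be followed longer than the current wording implies.
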